**1. TITLE PAGE**

Protocol Number: C-09-043/ NCT01497067

Medical Specialty: Surgical IOL

Project Name /Number: Angle-Supported Phakic Refractive IOL / 25-5223

Sponsor Name & Address:  
Alcon Research, Ltd.  
[name]  
[name]

Test Article(s) / Product(s):  
AcrySof® CACHET® Phakic Lens  
Models L12500, L13000, L13500 and L14000

Clinical Investigator:

---

Signature

Date

Name & Inv. #

[figure not shown]
Address

[figure not shown]
Telephone

As listed on the Statement  
of Investigator

[figure not shown]
In signing you agree that you have read, understand and will adhere to this protocol.

[figure not shown]
See last page for electronic approvals.

[figure not shown]

[figure not shown]

Study Phase:	Not applicable	
Financial Disclosure Information for U.S. FDA Submission to be Obtained?	 Yes  No	
Test Article(s) / Product(s):	AcrySof® CACHET® Phakic Lens (L-series)	
Study Dosage / Usage:	Intraocular lenses are implantable medical devices and are intended for long term use over the lifetime of the subject. The phakic intraocular lens may be removed as needed (e.g. cataract extraction).	
Active Ingredients:	Not applicable	
Route of Administration:	Not applicable	
Objective(s):	
The primary objective is to estimate the annualized endothelial cell loss rate (for up to 10 years following date of implantation) of subjects previously implanted with the ACRYSOF CACHET Phakic Lens (L-series) from clinical studies C-02-23, C-02-40, C-03-21 and C-05-57.
 
The secondary objective is to collect additional safety data that may identify risk factors for eyes with significant endothelial cell loss.
	
Study Population:	Subjects previously implanted with the ACRYSOF CACHET Phakic Lens (L-series) during clinical studies C-02-23, C-02-40, C-03-21 and C-05-57 (includes subjects who have had the lens explanted for any reason).	
Structure:	 Parallel Group	Duration of Treatment: Duration of Assessment:
	 Crossover	Number of Treatments: Number of Sequences: Number of Periods: Duration of Periods: Washout Between  Yes  No Periods:
	 Other	No control, open label study Duration of Treatment: Subjects to be followed for 5 to 7 years (10 years from the time of implantation).

Yes

No

Masking:

None

Observer-Masked

Patient-Masked

Double-Masked

Randomization:

Yes

No

Group Assignment Ratio:

Concurrent Control:

None

No Treatment

Placebo

Active

Other

Specify:  
Specify:

Estimated Total Sample Size: Required: N/A

Planned: Up to 1321 eyes

Statistical Rationale Provided:  Yes See Section 11

No

Variable(s): Primary Efficacy

- None

Secondary Efficacy

- None

Primary Safety

- Central endothelial cell density
- Adverse events

Adverse Events:

[figure not shown]
Both volunteered and elicited

Other:

Analyses: The primary objective is to estimate the annualized endothelial cell loss rate (for up to 10 years following date of implantation) of subjects previously implanted with the ACRYSOF CACHET Phakic Lens (L-series) from clinical studies C-02-23, C-02-40, C-03-21 and C-05-57.

[figure not shown]
Combining data from this study with the data from the subjects' previous studies, the rate of endothelial cell density loss between consecutive visits will be calculated via a paired analysis and descriptive statistics on those rates will be presented. [REDACTED]

[REDACTED] Also, the percentage endothelial cell density decrease for each eye from baseline (6 month visit in previous study) to each visit will be calculated via a paired analysis and descriptive statistics for the actual and annualized loss rates will be presented.

The secondary objective is to collect additional safety data that may identify risk factors for eyes with significant endothelial cell loss.

Descriptive statistics will be provided for central [REDACTED] endothelial cell densities, [REDACTED]

#### **4. INTRODUCTION**

Angle-supported Phakic intraocular lenses (IOLs) have been shown to be effective in the correction of myopia and have several benefits over refractive surgery, including reversibility. These IOLs, however, have been associated with complications including possible loss of corneal endothelial cells, pupil ovalization, pigment dispersion, inflammation, synechiae, cataractogenesis, and pupillary block (Kohnen 2010). Of particular concern is possible endothelial cell loss (ECL) which may lead to corneal decompensation. Several factors may lead to ECL, one is possible compression forces against anterior chamber structures. In this study, endothelial cell density [REDACTED]

[REDACTED] will be monitored to assess possible causes of ECL.

The ACRYSOF CACHET Phakic IOL is an angle-supported, single-piece, foldable, soft acrylic lens with a chemically bonded UV chromophore and a 6.0 mm meniscus optic. This lens is designed for placement in the anterior chamber to correct moderate to high myopia and provide subjects with a form of vision correction, comfort, and convenience not attainable with spectacles or contact lenses. Because the ACRYSOF CACHET Phakic Lens is foldable, it can be inserted through a small incision, thus reducing the likelihood of induced astigmatism. The mechanical properties of the ACRYSOF material, together with the design of the ACRYSOF CACHET Phakic Lens, should result in lower forces against the anterior chamber angle.

Phased clinical studies have been completed, or are ongoing, to assess the safety and effectiveness of the ACRYSOF CACHET Phakic IOL. Models SA3M25, SA3M13, and SA3M35 (the SA-series) were studied as part of European (EU) clinical investigations conducted under Protocol C-99-38 (EU Phase 1) and Protocol C-01-22 (EU Phase 2). Models RA6M13 and RA6M35 (the RA-series) were studied as part of the U.S. clinical investigation conducted under Protocol C-02-23 (U.S. Phase 1). Models L12500, L13000, L13500, and L14000 (the L-series) are being studied (two studies are complete) in four protocols: as part of an EU clinical investigation conducted under Protocol C-02-40 (EU Phase 3); a completed U.S. clinical investigation conducted under Protocol C-02-23 (U.S. Phase 1 (second eyes only) and Phase 2); a completed U.S. clinical investigation conducted under Protocol C-05-57 (U.S. Phase 3); and also as part of a Canadian clinical investigation conducted under Protocol

C-03-21 (Canada Phase 3). Interim data from these ongoing clinical trials were reported in Kohnen 2009 and Knorz 2011.

Based on the results available to date, the overall risks for subjects implanted with the ACRYSOF CACHET Phakic IOL are representative of known risks associated with intraocular surgery and the implantation of a phakic IOL. Continued monitoring of postoperative corneal health, including endothelial cell density and cell morphology, is recommended to ensure safety of the subject. Endothelial cell loss will be followed in this study to understand the long-term safety of the ACRYSOF CACHET Phakic IOL (L-series). Only L-series IOLs will be followed in this study since this is the model that will be submitted for market approval. The ACRYSOF CACHET Phakic IOL is marketed outside the United States.

A summary of clinically significant findings from non-clinical and clinical studies and a summary of known and potential risks and benefits to human subjects can be found in the Clinical Investigator's Brochure (CIB-0021; TDOC-0006479) for the ACRYSOF CACHET Phakic IOL family including the following models: Models SA3M25, SA3M13, and SA3M35 (the "SA" series, all with a 5.5 mm diameter optic size), Models L12500, RA6M13 / L13000, RA6M35 / L13500, and RA6M14 / L14000 (the "RA" series and "L" series all have a 6.0 mm diameter optic size).

## **5. OBJECTIVE(S)**

The primary objective is to estimate the annualized endothelial cell loss (ECL) rate (for up to 10 years following date of implantation) of subjects previously implanted with the ACRYSOF CACHET Phakic Lens (L-series) within clinical studies C-02-23, C-02-40, C-03-21 and C-05-57.

The secondary objective is to collect additional safety data that may identify risk factors for eyes with significant ECL.

[figure not shown]

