#### **10.4.1. PRIMARY SAFETY**

##### **10.4.1.1. CENTRAL ENDOTHELIAL CELL DENSITY**

Descriptive statistics for central endothelial cell density, for each scheduled visit (including data from previous studies), will be provided. Descriptive statistics for central endothelial cell density chronic change (actual and percent) from baseline (6 month visit in previous study) to each scheduled visit will be provided. Descriptive statistics for central endothelial cell density change (actual and percent) between consecutive scheduled visits will be provided. All tables will be generated separately for first implanted eye, second implanted eye, and for both implanted eyes combined. Descriptive statistics include mean, median, standard deviation, sample size, minimum, maximum and confidence limits.

The mean rate of endothelial cell density decrease will be calculated via a paired analysis in order to calculate the mean of the differences between each reporting period.

[figure not shown]

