##### 4.1.2.1. CHRONIC CHANGE FROM DAY 147-182 (MONTH 6 IN PREVIOUS STUDIES)

[figure not shown]
Descriptive statistics will be provided for each scheduled visit, for [REDACTED] central [REDACTED] endothelial cell density, for all eyes combined. The statistics presented for endothelial cell density (using the average from the analyzable images for each eye) will include mean, median, standard deviation, sample size, minimum, and maximum.

[figure not shown]
The percent change of mean endothelial cell density over time from Day 147-182 (Form 5 or 5A) in the previous studies to each visit in the current study will be calculated. The actual and annualized percent change of mean endothelial cell density from the Day 147-182 (Form 5 or 5A) exam to each scheduled visit in this study will be calculated and presented along with median, standard deviation, sample size, minimum and maximum. Tables presenting the mean, median, standard deviation, sample size, minimum and maximum of baseline (Form 5 or 5A in previous studies) endothelial cell density and cell density change from baseline to each scheduled visit in this study will be presented for all eyes combined.

[figure not shown]

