#### 4.1.2.2. POSTOPERATIVE CHANGE FROM PREOPERATIVE BASELINE

[figure not shown]
Descriptive statistics will be provided for change from preoperative baseline (in previous studies) to each scheduled visit in this study, for [REDACTED] central [REDACTED] endothelial cell density, for all eyes combined. The statistics presented will include mean, median, standard deviation, sample size, minimum and maximum. The percent change of mean endothelial cell density from preoperative baseline (Form 0 or 0A in previous study) to each scheduled postoperative visit (both in previous studies and this study) will be calculated to determine subjects who had  $\geq 30\%$  loss. A table showing the number and percent of eyes which had the onset of  $\geq 30\%$  endothelial cell loss (central [REDACTED]) from the preoperative level or central [REDACTED] of  $\leq 1500$  endothelial cells/mm^2 (occurring 6 months or later following implantation) will be presented.

[figure not shown]
In addition, the mean actual and annualized percent change of endothelial cell density (using the average from the analyzable images for each eye) of all subjects from baseline to each visit will be calculated and presented along with median, standard deviation, sample size, minimum and maximum. These tables will be presented for all eyes combined.

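### In the readable text the primary annualized loss rate is computed only from two readings per eye, no row is named as the primary estimate, and the Year 10 row can understate loss

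*Protocol*

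**What the plan says.** Protocol Section 5 sets one target: "The primary objective is to estimate the annualized endothelial cell loss (ECL) rate (for up to 10 years following date of implantation". The readable text then offers several calculations.

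- Protocol Summary, Analyses: "the rate of endothelial cell density loss between consecutive visits will be calculated via a paired analysis". After a redaction, the same paragraph gives the percentage decrease from the Month 6 baseline "to each visit will be calculated via a paired analysis and descriptive statistics for the actual and annualized loss rates will be presented".
- Protocol 10.4.1.1: "The mean rate of endothelial cell density decrease will be calculated via a paired analysis", taken over reporting periods. It adds "All tables will be generated separately for first implanted eye, second implanted eye, and for both implanted eyes combined".
- SAP 4.1.2.1: "The actual and annualized percent change of mean endothelial cell density from the Day 147-182 (Form 5 or 5A) exam to each scheduled visit".
- SAP 4.1.2.2, on change from the preoperative baseline: "the mean actual and annualized percent change of endothelial cell density", from baseline to each visit.

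No readable sentence says which visit, baseline or summary answers the objective, or whether annualizing is simple or compound.

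Three further provisions matter. Protocol 10.2.1 and SAP 3.1.1 remove density data collected after explantation (without replacement by another L-series lens) from the main analyses. Protocol 9.3.7 asks investigators to consider explantation when central density comes near 1500 cells/mm². Protocol 10.6 and SAP 3.1.2 rule out imputation.

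**The concern.** This is an uncontrolled, estimation-only safety study, so the loss rate is its main result. A two-reading rate to a given visit uses the baseline and that visit and ignores every reading between them. It also uses only the eyes read at that visit, so each row describes a different set of eyes.

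The Year 10 row matters most because it spans the period in the objective. An eye that loses cells fast, reaches a low density and is explanted at Year 7 contributes nothing to it, although its on-lens readings up to Year 7 were collected and are evaluable. If such removals are linked to fast loss, the remaining eyes look better than the full cohort. For a safety rate that is the unfavourable direction of error.

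**Working it through.** **Inputs from the documents.** Protocol Table 17-1 schedules Year 4, Year 5, then half-yearly visits to Year 10: 12 visits. With Month 6 that makes 13 readings. The maximum is 1321 eyes in 778 subjects (Protocol Section 11). The required sample size is N/A, and no SD, expected rate, precision target or retention is given, so there is no planned figure to reproduce.

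**Assumptions.** Reading error s = 4–8% of density; between-eye slope SD b = 1–2 %/year; near-linear loss; eyes treated as independent in both methods.

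**1. Number of candidate rates.** The SAP gives 12 visits × 2 baselines = 24 annualized means. The protocol adds 12 − 1 = 11 in-study consecutive-visit rates, and its tables come in three eye groupings.

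**2. Does the choice move the answer?**
- With a true constant 2 %/year, s = 5, b = 1 and 1321 eyes, the lowest and highest of the 12 Month 6-based means averaged 1.96 and 2.04. For the 11 consecutive-visit means they averaged 1.39 and 2.63.
- The baseline matters more. Take 2% compound loss, simple annualizing and an assumed 5% early loss:
  - Month 6 to Year 4: (1 − 0.98^3.5)/3.5 = 1.95 %/year
  - Month 6 to Year 10: (1 − 0.98^9.5)/9.5 = 1.84
  - Preoperative to Year 4: (1 − 0.95 × 0.98^3.5)/4 = 2.87
  - Preoperative to Year 10: (1 − 0.95 × 0.98^9.5)/10 = 2.16

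**3. Precision with full retention.**
- Two-reading rate, Month 6 to Year 10: Var = (2s²/9.5² + b²)/n.
- All-readings slope: Var = (s²/Sxx + b²)/n, with Sxx = 80.27 for years 0.5, 4, 5, 5.5, …, 10.
- s = 5, b = 1: 50/90.25 = 0.554 and 25/80.27 = 0.311. The SE ratio is √(1.554/1.311) = 1.09. The 95% half-widths at n = 1321 are 1.96√(1.554/1321) = 0.067 and 1.96√(1.311/1321) = 0.062 %/year.
- s = 4, b = 2: √(4.355/4.199) = 1.02. s = 8, b = 1: √(2.418/1.797) = 1.16.
- The documents do not list parent-study visits between Month 6 and Year 4. If readings at Years 1, 2 and 3 are assumed, Sxx = 135.94 and the last ratio becomes √(2.418/1.471) = 1.28.
- At s = 5, b = 1 the ratio is 1.97 for Month 6 to Year 4 and 12.4 for one six-month pair (half-width 0.76 %/year).

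**4. Precision with attrition.** The Year 10 row loses whole eyes; the slope keeps their earlier readings. At s = 5, b = 1, the SEs are 0.0410 against 0.0334 at 70% retention (ratio 1.23) and 0.0485 against 0.0348 at 50% (ratio 1.39). Over 50–90% retention and the assumed s and b, the range is about 1.15–1.6.

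**5. Selection by explantation (simulation).** Assumed: Month 6 density about 2700, mean loss 2 %/year, 5% reading error, and removal after the first reading below a threshold.
- Threshold 1500, b = 1–2: about 1–5% of eyes removed; Year 10 two-reading mean 1.81–1.98.
- Threshold 1700, b = 2: about 14% removed in one run; mean 1.56–1.62 across runs.
- The mixed model on all on-lens readings gave about 2.0 throughout.

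**The case against.** **Redaction.** Text is blacked out directly after the consecutive-visit rate in the Protocol Summary. Nine consecutive entries are redacted in the Protocol's contents list between 10.4.1.2 and 10.6. A redacted SAP entry starts on page 11, between 4.1.2 (page 10) and 4.2 (page 15). A longitudinal model or a named primary summary could sit in any of these. This stands: the point concerns the readable text, and the fix must be conditional.

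**Selectability.** A reader might infer that the sponsor is free to pick its answer from many rates. The documents do not support that. Hidden text may name the estimate, every row is to be tabulated, Protocol 10.7 plans no test to win by selection, and the chronic analysis is tied to the Month 6 baseline. Under constant loss the Month 6-based rows barely differ.

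**Precision.** A reader might also infer that the result is much less precise than it could be. That is true of the consecutive-visit rates and often of early visits, but not of Month 6 to Year 10. There most of any loss of precision comes from attrition, and the documents give no retention figure. With 1321 eyes both half-widths are small in absolute terms.

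**Preference.** By-visit description is legitimate in an uncontrolled follow-up and shows non-constant loss directly. That is a reason to keep the tables, not to do without a named primary estimate. The warning about unscheduled readings is also right: Protocol 9.3.7 allows more frequent examination of eyes that are low or losing cells, so those readings would cluster in the worst eyes.

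**Conclusion.** The point holds in limited form. In the readable plan the primary rate comes only from two-reading comparisons, no row is designated as the answer, and the natural candidate drops eyes that left or were explanted.

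The understatement is small if removals are rare (1.81–1.98 against 2 %/year in the simulations with a 1500 threshold) and larger if they are common (1.56–1.62 with a 1700 threshold and slope SD 2). The Year 10 standard error is about 1.0–1.2 times that of an all-readings slope with full retention and about 1.15–1.6 times with 50–90% retention. Reading error, slope SD, retention, starting density and the removal rule behind these sizes are assumptions, and pairing of eyes was ignored. Whether the redacted pages already settle the matter cannot be judged from the public text.

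**What to change.** First check whether the redacted sections already name a primary estimate of this kind. If they do not, add one paragraph to Protocol 10.4.1.1 and SAP 4.1.2:

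- **Primary estimate:** mean slope of log central endothelial cell density per year from Month 6 onward, reported as percent per year with a 95% confidence interval. The protocol promises confidence limits for density; the readable SAP lists omit them.
- **Model:** linear mixed model with random intercept and slope for eye within subject.
- **Data:** all scheduled on-lens readings from the parent studies and this study, at their actual day.
- **Checks:** a test for change in slope over time, and a sensitivity analysis adding unscheduled readings.
- **Existing tables:** keep them, labelled as descriptive.

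The cost is one model on data already being collected. The downside is that the headline rate assumes roughly constant proportional loss, which the slope check examines, and dropout that depends only on observed readings, which the data cannot fully test.

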## **6. TEST ARTICLE(S)**

### ***6.1. Identification***

Lenses will not be supplied during this clinical trial, as subjects invited to enroll will have been previously implanted with the ACRYSOF CACHET Phakic Lens (L-series) from clinical studies C-02-23, C-02-40, C-03-21 and C-05-57.

The ACRYSOF CACHET Phakic Lens is an angle-supported, anterior chamber, single piece lens composed of a cross-linked soft acrylic polymeric material with a chemically bonded UV-absorber. This is the same acrylic material that is currently used in the optic of the globally marketed ACRYSOF multi- and single-piece IOL Models MA30BA, MA60BM, SA30AL, and SA60AT.

The ACRYSOF CACHET Phakic Lens models have a 6.0 mm diameter meniscus optic and are intended for implantation in the anterior chamber angle. The overall lengths of these models vary from 12.5 mm to 14.0 mm as follows: Models L12500 (12.5 mm), L13000 (13.0 mm), L13500 (13.5 mm) and L14000 (14.0 mm). The dioptric range of these IOLs is -6 to -16.5D.

## **6.2. Usage**

The ACRYSOF CACHET Phakic Lens is a permanent implantable medical device, thus the expected duration of individual subject use, and exposure, is expected to be for the remainder of the subject's life, or until cataract extraction is needed.

[figure not shown]
## **6.3. Test Article Accountability Procedures**

Damaged test articles or explanted lenses must be packaged in a biohazard bag and returned to the sponsor at the following address:

Attn: [REDACTED]

Mail Code: [REDACTED]

Alcon Research, Ltd.  
[name],  
[name]

In cases of explanted lenses, all information related to the adverse device effect or serious adverse event should be entered into the EDC system on the *Adverse Device Effect and Serious Adverse Event Form* within 24 hours of the investigator's or site's awareness of the event. Please include a printed copy of the completed *Adverse Device Effect and Serious Adverse Event Form* with product returns.

Refer to Section 12 for additional information on reporting any [REDACTED], adverse device effects, or serious adverse events.

## **7. SUBJECTS**

### ***7.1. Subject Population***

Subjects previously implanted (unilaterally or bilaterally) with the ACRYSOF CACHET Phakic Lens (L-Series) in clinical studies C-02-23, C-02-40, C-03-21 and C-05-57 (includes subjects who have had the lens explanted for any reason). Up to 778 subjects will be enrolled; up to 65 subjects per site. No vulnerable population is planned.

### ***7.2. Inclusion Criteria***

1. Subjects previously implanted (including subjects who have had the lens explanted for any reason) with an ACRYSOF CACHET Phakic Lens (L-Series) from clinical studies C-02-23, C-02-40, C-03-21 and C-05-57 and are eligible for continued follow-up (ie, exited from their previous study).
2. Subjects are willing and able to complete the yearly postoperative study visits.
3. Subjects are able to understand and sign a statement of informed consent.

[figure not shown]
### ***7.3. Exclusion Criteria***

None

## **8. STUDY DESIGN**

### ***8.1. Study Design***

Subjects enrolled in this study will attend postoperative visits for up to 10 years following the date of implantation and will be able to enroll at any time for the duration of this trial. These subjects will be followed postoperatively to Year 10/10A (3619 – 3740 days) at appropriate intervals as defined in Section 9.1.

